#### 8 ASSESSMENT OF SAFETY

#### **8.1** Adverse Events

AEs will be monitored from the time that the subject and parent(s)/legal representative signed the informed consent and throughout the study (see Section 3.5 for a definition of the study duration) and will be elicited by direct, non-leading questioning or by spontaneous reports. Further details for AE reporting can be found in Section 8.1.2.

# 8.1.1 Definition of an Adverse Event

An AE is the development of an undesirable medical condition or the deterioration of a preexisting medical condition following or during exposure to a pharmaceutical product, whether or not considered causally related to the product. An undesirable medical condition can be symptoms (e.g. nausea, chest pain), signs (e.g. tachycardia, enlarged liver) or the abnormal results of an investigation (e.g. laboratory findings, electrocardiogram). In clinical studies, an AE can include an undesirable medical condition occurring at any time, including run in or washout periods, even if no IMP has been administered.

This definition includes events occurring from the time of the subject giving informed consent until the end of the study (as defined in Section 3.5).

# 8.1.2 Categorisation of Adverse Events

#### 8.1.2.1 Intensity Classification

AEs will be classified as mild, moderate or severe according to the following criteria:

- Mild: symptoms do not alter the subject's normal functioning
- **Moderate**: symptoms produce some degree of impairment to function, but are not hazardous, uncomfortable or embarrassing to the subject
- **Severe**: symptoms definitely hazardous to well-being, significant impairment of function or incapacitation.

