# 8.6 Symptom Scale

This scale will be completed by the subject/caregiver at Visit 1, after treatment intake (Table 11). Subjects/caregivers will rate their overall experience of stomach cramping, stomach bloating and nausea on a 5-point scale, with 1=no symptoms, 2=mild, 3=bothersome, 4=distressing and 5=severely distressing symptoms. Symptoms rated from mild (2) to severely distressing (5) must be reported as an AE.

Symptom 1=no symptoms 2=mild 3=bothersome 4=distressing 5=severely distressing

Stomach cramping Stomach bloating Nausea

Table 11 Symptom Scale

PAGE 55/103

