**PAGE 59/103** 

All AEs will be coded according to the MedDRA and will be classified by MedDRA preferred term and system organ class. AE listings will be presented by subject, system organ class and preferred term.

Incidence of all reported TEAE and SAEs will be tabulated by treatment group and overall. In addition, summary tables will be presented by maximum intensity, drug relationship and AEs/TEAEs associated with premature withdrawal of study medication.

A TEAE is defined as any AE that occurs during the active phase of the study if:

- It was not present prior to receiving the first dose of IMP, or
- It was present prior to receiving the first dose of IMP but the intensity increased during the active phase of the study.

All TEAEs will be flagged in the AEs listings.

Concomitant medication will be coded by using World Health Organisation (WHO) Drug Dictionary and will be summarised by treatment group and overall with the number and percentage of subjects receiving concomitant medication by drug class and preferred drug name.

Summary statistics (mean, median, SD and range as appropriate) by treatment group and overall will be presented for vital signs, BP, HR, clinical laboratory tests (blood and urine sample), physical examination, etc. at each assessment with change from Baseline. For laboratory data, abnormal values will be flagged in the data listings and a list of clinically significant abnormal values will be presented. Shift tables will be presented of the number and percentage of subjects with low, normal or high values and normal or abnormal exams.

Frequency count with two-sided 95%CI when appropriate by treatment group and by overall will be presented for symptom questionnaire data (stomach cramping, stomach bloating and nausea) on a 5-point scale (see Table 11).

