1.4.2.2 Safety assessments

- Adverse events (AEs) occurring during the study, from signature of informed consent up to 30 days after colonoscopy (collected at Visit 4 Day 32 -5/+15), and with the following categorizations:
 - Seriousness (Yes/No),
 - Intensity (Mild/Moderate/Severe),
 - Causality (i.e. relationship to study treatment, as Related/Not related).
- Tolerability by a Symptom Scale after each dose of treatment. Subjects/caregivers will rate the preparation related symptoms after intake (stomach cramping, stomach bloating and nausea) on a paediatric 5-point scale, with 1=no symptom, 2=mild, 3=bothersome, 4=distressing and 5=severely distressing symptoms.
- Description and histological examination of any colonic biopsy specimens of mucosal lesions suspected by the investigator to have been caused by colonic lavage.
- Vital signs including body weight and physical examination: (systolic and diastolic) blood pressure (BP) and heart rate (HR) will be assessed with an automated device so that measurements are independent of the observer. BP and HR will be recorded in standing position and after 5 minutes rest in supine position at V1, after 5 minutes rest in supine position at V2 and V4. Absolute values and change from Baseline (V1) will be analysed. Body temperature and weight will be recorded at V1, V2 and V4.
- Local laboratory data at V1, V2 and V4:
 - Serum biochemistry including: anion gap, alanine aminotransferase (ALT), aspartate aminotransferase (AST), creatine phosphokinase (CPK), lactic dehydrogenase (LDH), gamma-glutamyl transferase (GGT), total and conjugated bilirubin, creatinine, urea, serum electrolytes (sodium, potassium, chloride, calcium, magnesium, phosphate, bicarbonate), alkaline phosphatase, albumin, total protein, C reactive protein (CRP), uric acid, creatinine clearance, eGFR (calculated in the eCRF using the Schwartz bedside equation [1]: eGFR = 0.41 * height (cm)/S_{cr} (mg/dl), where S_{cr} is the serum creatinine) and osmolality.

IPSEN GROUP

SAP final version 4.0: 25 August 2020

- Urinalysis by dipstick including pH, protein, ketones, bilirubin, blood, urobilinogen, nitrites, leukocytes, glucose and specific gravity microscopic examination.
- Blood and urine sulfates dosages by central laboratory at V1, V2 and V4.

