3.2.2.1 Adverse events

All AEs will be coded according to MedDRA (last version used for coding during the study course) and will be classified by MedDRA preferred term (PT) and system organ class (SOC). AE listings will be presented by subject, SOC and PT for all AEs, serious AEs (SAEs) and AEs leading to withdrawal on the safety population.

A TEAE is defined as any AE that occurs during the active phase of the study if:

it was not present prior to receiving the first dose of IMP

or

• it was present prior to receiving the first dose of IMP but the intensity increased during the active phase of the study.

All TEAEs will be flagged in the AEs listings.

An overall summary table of all AEs will be presented with the number of AEs and the numbers and percentage of subjects with exact 95 % CI for each of the following categories:

- Any AEs,
- Any SAEs,
- Causality of SAEs,
- Any TEAEs,
- Intensity of TEAEs,
- Causality of TEAEs,
- Causality and intensity of TEAEs,
- Any TEAEs leading to death,
- Any TEAEs leading to withdrawal.

In the event of multiple AEs being reported by the same subject, each subject is counted for each intensity level, each causality level or each intensity and causality combined level. That means that the total number of subjects for all levels of intensity/causality might be higher

than the overall number of subjects with at least one AE. Related adverse events are those events with causality missing or related.

Incidence by SOC/PT of all reported TEAEs, related TEAEs, SAEs and TEAEs leading to withdrawal of study medication will be tabulated by treatment group and overall. In addition, summary tables by SOC/PT will present TEAEs by maximum intensity and drug relationship and will present TEAEs with incidence ≥ 2 %. And a summary table will present TEAEs by decreasing frequency of PT.

In the event of multiple occurrence of the same AE (same PT) being reported by the same subject, the maximum intensity (severe > missing > moderate > mild) and the most serious causality (related > not related) for each concerned PT will be chosen.

Moreover, the summary table will be duplicated by sex, age class and weight class, as well as the summary table of the incidence of TEAEs by SOC and PT.

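### The moderate adverse event grade excludes uncomfortable or embarrassing symptoms, so such a symptom with some impairment fits no grade and may be graded inconsistently

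*Protocol*

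**What the plan says.** Protocol 8.1.2.1 rules that "AEs will be classified as mild, moderate or severe according to the following criteria". The three criteria, in order, come to this:

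- An event is mild if the subject functions as usual.
- For the middle grade, moderate, the protocol's own words are "symptoms produce some degree of impairment to function, but are not hazardous, uncomfortable or embarrassing to the subject".
- The top grade, severe, needs definite hazard, a significant loss of function, or incapacitation.

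Protocol 8.6 has subjects or caregivers rate stomach cramping, stomach bloating and nausea from 1 to 5 after intake, and then requires: "Symptoms rated from mild (2) to severely distressing (5) must be reported as an AE". It does not say how a score of 2 to 5 relates to the three intensity grades.

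The grade is used in the analysis. Protocol 10.4.7 states that "summary tables will be presented by maximum intensity, drug relationship". SAP 3.2.2.1 states that "summary tables by SOC/PT will present TEAEs by maximum intensity and drug relationship", and its overall summary also counts treatment-emergent adverse events (TEAEs) by intensity and by causality crossed with intensity. SAP 1.4.2.2 repeats the three labels without defining them.

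Separately, SAP 3.2.2.4 tabulates cramping, bloating and nausea on the 5-point Symptom Scale after each dose by treatment group. Those tables do not use the adverse event grade.

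**The concern.** An intensity scale should give every event one grade. Here the middle grade carries a condition that many expected effects of a bowel preparation cannot meet. Cramping, bloating and nausea are unpleasant to the person who has them, and the upper levels of the Symptom Scale are worded in terms of how bothersome or distressing the symptom is. If such a symptom also interferes somewhat with normal function, the definitions offer no place for it.

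Comparing safety and tolerability is a secondary objective (Protocol 2.2.2), and about 25 centres are planned (Protocol 3.1). If each investigator resolves the gap privately, part of what the TEAE intensity tables show will be how the definition was read. The phrase may have been meant to say that moderate symptoms are not hazardous but may be uncomfortable or embarrassing, which is the opposite instruction. Nothing in the documents settles which was intended.

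**Working it through.** No sample size, power or rate is at issue, so there is no stated figure to reproduce. The check is whether the three definitions cover all cases.

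**Step 1: list the cases.** The definitions in Protocol 8.1.2.1 use four attributes: impairment (none, some, significant), and hazardous, uncomfortable and embarrassing (each yes or no). That gives 3 × 2 × 2 × 2 = 24 combinations. I treat incapacitation as significant impairment, and the hazard named under moderate and under severe as the same attribute.

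| Impairment | Hazardous | Uncomfortable / embarrassing | Combinations | Grade as written | Grade if moderate excludes only hazard |
|---|---|---|---|---|---|
| none | no | any | 4 | mild | mild |
| none | yes | any | 4 | mild and severe | mild and severe |
| some | no | neither | 1 | moderate | moderate |
| some | no | one or both | 3 | **no grade** | moderate |
| some | yes | any | 4 | severe | severe |
| significant | any | any | 8 | severe | severe |

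Check: 4 + 4 + 1 + 3 + 4 + 8 = 24. As written, 3 combinations have no grade. If moderate excludes only hazardous events, none is left ungraded. The 4 combinations that fit both mild and severe are a separate overlap, present either way. These are counts of logical cases, not shares of events.

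**Step 2: do real events reach the gap?** A cramping, bloating or nausea score of 2 to 5 becomes an adverse event under Protocol 8.6 and must then be graded under 8.1.2.1. If it causes no impairment it is mild. If impairment is significant it is severe. With some impairment and discomfort it falls in the ungraded row. No other section of the protocol or SAP supplies a rule for that row.

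**Step 3: where does the grade go?** When the same preferred term recurs in a subject, SAP 3.2.2.1 keeps the maximum intensity, ranking severe above missing above moderate above mild. A subject's entry for nausea can therefore change according to whether an investigator chose mild, moderate or severe, or left the field blank if the eCRF permits that.

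**Step 4: how many events?** The documents do not allow a count.

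- The ceiling on ratings is 250 subjects × 3 symptoms × 2 doses = 1500. This is not a count of adverse events: a score of 1 is not reported, a repeat is recorded a second time only if recovery between instances is documented (Protocol 8.1.3), and the maximum-intensity tables keep one grade per subject and preferred term.
- If 10% to 50% of subjects had an uncomfortable symptom with some impairment, that would be 0.10 × 250 = 25 to 0.50 × 250 = 125 subjects. The range is an assumption with no anchor in the documents.
- The only related rate is for gastrointestinal TEAEs in the adult studies, 4.5% and 4.3% (Protocol 1.3). Applied here, 0.045 × 250 is about 11 subjects. That is another population, possibly under another reporting rule, and it covers all gastrointestinal events rather than only those in the gap.

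**The case against.** The strongest reply is that each definition turns first on function, so a sensible investigator will grade on function and choose moderate. Some will. But that sets aside a written criterion, and a colleague at another site may apply it. The possibility of both is the point.

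Three further replies stand and limit the point:

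- The wording is the same in both arms, and nothing shows a differential effect on the treatment comparison.
- Only the middle band is exposed. Uncomfortable symptoms with no impairment are mild, and those with significant impairment are severe.
- The severity of cramping, bloating and nausea is already reported elsewhere. SAP 3.2.2.4 gives each symptom by dose and arm, adds a total score, and breaks the symptoms down by nasogastric tube use, sex, age class and weight class. This does not repair the TEAE intensity tables and does not cover other uncomfortable events such as vomiting, but it means that tolerability of these three symptoms does not rest on the adverse event grade.

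A reader might also count diarrhoea among the events that section 8.6 brings in. It is not on the Symptom Scale, so that section does not do so.

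**Conclusion.** The point holds as a gap in a definition. Read literally, Protocol 8.1.2.1 gives no grade to an uncomfortable or embarrassing symptom with some, but not significant, impairment. Because cramping, bloating and nausea scored 2 to 5 must be reported as adverse events, and TEAEs are tabulated by intensity and maximum intensity, such events may be graded inconsistently between investigators and sites. The extent and direction are unknown. TEAE incidence, seriousness, causality, the primary endpoint and the Symptom Scale tables are not affected.

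A reader might infer that these events must be moved to mild or severe, and that the intensity tables are therefore unreliable. The documents do not support that. Mild and severe do not fit these events either, no section directs such a move, and an investigator may still choose moderate. What follows is a risk of inconsistent grading, not a demonstrated failure of the tables. Nor do the documents support any figure for the number of subjects affected.

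The conclusion assumes that the moderate definition is read as excluding each of the three attributes it names.

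**What to change.** In Protocol 8.1.2.1, delete *uncomfortable or embarrassing* from the moderate definition, so that moderate means some impairment that is not hazardous. Issue a short note to sites. The deletion closes all 3 ungraded combinations. It leaves the mild/severe overlap for hazardous events without impairment, which would need its own sentence on which grade takes precedence.

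For events graded under the present wording, state the limitation in the clinical study report and read the TEAE intensity tables for cramping, bloating and nausea beside the Symptom Scale tables already planned in SAP 3.2.2.4. No new table is needed.

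The cost is one phrase, one note and a few sentences in the report. The drawback is that events graded before and after the change are not strictly comparable, so the date of the change must be documented. Timing also matters: the current protocol is dated 02 March 2020 with a planned end in Q2 2020, and SAP version 4.0 is dated 25 August 2020. If collection is complete, only the reporting part of the fix remains useful.

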#### 8.1.2.2 Causality Classification

The relationship of an AE to IMP administration or comparator will be classified according to the following:

- **Related**: reports including good reasons and sufficient information (e.g. plausible time sequence, dose response relationship, pharmacology, positive dechallenge and/or rechallenge) to assume a causal relationship with IMP administration in the sense that it is plausible, conceivable or likely.
- **Not related**: reports including good reasons and sufficient information (e.g. implausible time sequence and/or attributable to concurrent disease or other drugs) to rule out a causal relationship with IMP administration.

# 8.1.2.3 Assessment of Expectedness

The expectedness of an AE shall be determined by the sponsor according to the IB for an unapproved IMP, or the SmPC or package insert (PI) for an authorised medicinal product that is being used according to the terms and conditions of the marketing authorisation. If the IMP or comparator has marketing authorisations in several countries with different SmPCs or PIs, one will be selected as the reference document for assessing expectedness.

The reference document for assessing expectedness of AEs/event in this study will be the current IB.

PAGE 50/103

#### 8.1.2.4 Laboratory Test Abnormalities

Abnormalities in laboratory test values should only be reported as AEs if any of the following apply:

- They require intervention or a diagnosis evaluation to assess the risk to the subject
- They are considered as clinically significant by the investigator.

# 8.1.2.5 Abnormal Physical Examination Findings

Clinically significant changes, in the judgement of the investigator, in physical examination findings (abnormalities) will be recorded as AEs.

# 8.1.2.6 Other Investigation Abnormal Findings

Abnormal test findings as judged by the investigator as clinically significant (e.g. electrocardiogram changes) that result in a change in IMP dosage or administration schedule, or in discontinuation of the IMP, or require intervention or diagnostic evaluation to assess the risk to the subject, should be recorded as AEs.

# 8.1.3 Recording and Follow-up of Adverse Events

At each visit, the subject should be asked a non-leading question such as: "How have you felt since starting bowel cleansing or the last visit/assessment?"

All observed or volunteered AEs, regardless of treatment group or suspected causal relationship to IMP or comparative treatment will be recorded on the AE page(s) of the eCRF.

Each instance of adverse events that occur twice in the split dose regimen (e.g. nausea) will be recorded twice on the eCRF, if recovery is documented between both instances.

Events involving drug reactions, accidents, illnesses with onset during the treatment phase of the study, or exacerbation's of pre-existing illnesses should be recorded.

Any AEs already recorded and designated as 'continuing' should be reviewed at each subsequent assessment.

For all AEs, the investigator must pursue and obtain information adequate both to determine the outcome of the AE and to assess whether it meets the criteria for classification as an SAE requiring immediate notification to the sponsor or its designated representative. For all AEs, sufficient information should be obtained by the investigator to determine the causality of the AE (i.e. IMP or other illness). The investigator is required to assess causality and record that assessment on the eCRF. Follow-up of the AE, after the date of IMP discontinuation, is required if the AE or its sequelae persist. Follow-up, that will include medical care, is required until the event or its sequelae resolve or stabilise at a level acceptable to the investigator and the sponsor's clinical monitor or his/her designated representative.

# 8.1.4 Reporting of Serious Adverse Events

All SAEs (as defined below) regardless of treatment group or suspected relationship to IMP or comparator must be reported immediately (within 24 hours of the investigator's knowledge of the event) to the pharmacovigilance contact specified at the beginning of this protocol. If the immediate report is submitted by telephone, this must be followed by detailed written reports using the SAE report form.

An SAE is any AE that:

(1) Results in death,

PAGE 51/103

- (2) Is life-threatening, that is any event that places the subject at immediate risk of death from the event as it occurred. It does not include an event that, had it occurred in a more severe form, might have caused death,
- (3) Results in in-patient hospitalisation or prolongation of existing hospitalisation, excluding admission for social or administrative reasons (see further),
- (4) Results in a persistent or significant disability/incapacity, where disability is a substantial disruption of a person's ability to conduct normal life functions,
- (5) Results in congenital anomaly/birth defect in the offspring of a subject who received the IMP,
- (6) Is an important medical event that may not result in death, be life-threatening, or require hospitalisation but which, based upon appropriate medical judgement, may jeopardise the subject and may require medical or surgical intervention to prevent one of the outcomes listed in this definition. Examples of such medical events include allergic bronchospasm requiring intensive treatment in an emergency room or at home, blood dyscrasias or convulsions that do not result in in-patient hospitalisation, or the development of drug dependency or drug abuse.

In addition to the above criteria, any additional AE that the sponsor or an investigator considers serious should be immediately reported to the sponsor and included in the corporate SAEs database system.

- Hospitalisation is defined as any in-patient admission (even if less than 24 hours). For chronic or long term in-patients, in-patient admission also includes transfer within the hospital to an acute/intensive care in-patient unit.
- **Prolongation of hospitalisation** is defined as any extension of an in-patient hospitalisation beyond the stay anticipated/required in relation to the original reason for the initial admission, **as determined by the investigator or treating physician**. For protocol-specified hospitalisation in clinical studies, prolongation is defined as any extension beyond the length of stay described in the protocol. Prolongation in the absence of a precipitating, treatment emergent, clinical AE (i.e. not associated with the development of a new AE or worsening of a pre-existing condition) may meet criteria for "seriousness" but is not an adverse experience and thus is not subject to immediate reporting to the sponsor.
- Preplanned or elective treatments/surgical procedures should be noted in the subject's screening documentation. Hospitalisation for a preplanned or elective treatment/surgical procedure should not be reported as an SAE unless there are complications or sequelae which meet the criteria for seriousness described above.

Any SAE must be reported immediately (within 24 hours), independent of the circumstances or suspected cause, if it occurs or comes to the attention of the investigator at any time during the study period.

Any AE/SAE with a suspected causal relationship to IMP administration or comparator occurring at any other time after completion of the study must be promptly reported.

The following information is the minimum that must be provided to the sponsor pharmacovigilance contact within 24 hours for each SAE:

- Study number
- Centre number
- Subject number

PAGE 52/103

- AE
- Investigator's name and contact details

The additional information included in the SAE form must be provided to the sponsor or representative as soon as it is available. The investigator should always provide an assessment of causality for each event reported to the sponsor. Upon receipt of the initial report, the sponsor will ask for the investigator's causality assessment if it was not provided with the initial report.

The investigator should report a diagnosis or a syndrome rather than individual signs or symptoms. The investigator should also try to separate a primary AE considered as the foremost untoward medical occurrence from secondary AEs which occurred as complications.

